**Main Analytical Approach**

- **ORR:** The number and percentage of participants with the best confirmed response in the following response categories at will be summarized by treatment arm: sCR, CR, VGPR, PR, overall response (sCR+CR+VGPR+PR), minimal response (MR), stable disease (SD), progressive disease (PD), and not evaluable (NE). The corresponding exact 95% CI for ORR will also be provided. Participants with unknown or missing responses will be treated as non-responders, i.e., these participants will be included in the denominator when calculating percentages of response. The exact 95% CI for the difference will be calculated.
- **CBR:** summaries of CBR by treatment arms will be provided in the same way as ORR.
- **DoR:** Distribution of DoR will be summarized using the Kaplan-Meier method by treatment arm. The median, 25th and 75th percentiles of DoR will be estimated and corresponding 95% confidence intervals will be estimated using the Brookmeyer-Crowley method [Brookmeyer, 1982].
- **TTR:** TTR will be summarized descriptively by treatment arm using medians and quartiles in the subset of participants with a confirmed response of PR or better as the Best Overall Response (BOR).
- **TTP:** Distribution of TTP will be summarized using the Kaplan-Meier method by treatment arm. The median, 25th and 75th percentiles of TTP will be estimated and corresponding 95% confidence intervals will be estimated using the Brookmeyer-Crowley method [Brookmeyer, 1982]. TTP analysis will also be conducted using Cox proportional hazards model stratified by randomization factors. Refer to Section 4.2.3 for details of the analytical approaches.
- **MRD Negativity Rate:** For MRD negativity rate based on bone marrow testing using Next Generation Sequencing (molecular negativity), the number and percentage of participants who have achieved MRD negativity will be summarized by treatment arm. For analysis purposes, participants in the ITT population without MRD assessment will be considered as having positive MRD. The corresponding exact 95%

CI for MRD negativity rate will also be provided. Number and percentage of participants who have sustained MRD negativity ( $\geq 6$  months,  $\geq 12$  months) will be provided. Information of MRD will be included in the listing of response. If data are available, imaging-based assessment of MRD (i.e. PET-CT) will also be included in the listing and related to NGS testing.

#### **4.3.2.2. Supplementary analyses**

Additional analyses of DoR will be conducted for the supplementary estimand of DoR.

#### **4.3.3. Pharmacokinetic Analyses**

Plasma concentrations of belantamab mafodotin, total mAb, and cys-mcMMAF will be summarized using descriptive statistics, graphically presented (where appropriate) and listed based on the Pharmacokinetic (PK) Analysis Set. Details of the planned displays are provided in the Output and Programming Specification (OPS) document.

#### **4.3.4. Immunogenicity (Anti-Drug Antibody) Analyses**

For each subject, the anti-belantamab mafodotin antibody results, titers, and neutralizing antibody assay results, and total antibody concentration will be listed for each assessment time point. The frequency and percentage of participants with positive and negative anti-drug antibody and neutralizing antibody assay results will be summarized for each assessment time and overall for each subject by dose cohort. The conclusive results will be based on the total antibody concentration. The immunogenicity analyses will be based on the Safety Analysis Set.

#### **4.3.5. Secondary Patient Reported Outcome Analyses**

The EORTC QLQ-C30 (version 3.0), EORTC QLQ-IL52 (disease symptom domain of EORTC QLQ-MY20), EORTC QLQ-MY20 and the PRO-CTCAE are three oncology-specific Health-Related Quality-of-Life (HRQoL) assessments that will be analysed in this study as supportive secondary endpoints. EORTC QLQ-IL52 will be included in the EORTC QLQ-MY20 analyses.

In addition, the impact of potential corneal event on function and health-related quality-of-life will be assessed with the Ocular Surface Disease Index (OSDI) visual function questionnaire as a supportive secondary endpoint.

The analysis of EORTC QLQ-C30 and EORTC QLQ-MY20 (including EORTC QLQ-IL52) will be based on the ITT Analysis Set; while the analysis of PRO-CTCAE, and OSDI will be based on the Safety Analysis Set.

#### ***Patient Reported Outcome Version of the Common Term Criteria for Adverse Events (PRO-CTCAE)***

The Patient-Reported Outcomes Version of the Common Terminology Criteria for Adverse Events (PRO-CTCAE) is a patient-reported outcome measure developed to

evaluate symptomatic toxicity in patients on cancer clinical trials [Basch, 2014]. The PRO-CTCAE was designed to be used as a companion to the Common Terminology Criteria for Adverse Events (CTCAE), the standard lexicon for adverse event reporting in cancer trials. The PRO-CTCAE includes an item library of 124 items representing 78 symptomatic toxicities drawn from the CTCAE. PRO-CTCAE provides a systematic yet flexible tool for descriptive reporting of symptomatic treatment side effects in cancer clinical trials. In the present study, a subset of items selected from the PRO-CTCAE Version 1.0 Item library will be administered.

The levels and related code values for PRO-CTCAE are shown below:

	Levels and related code values				
Response scale	0	1	2	3	4
Frequency	Never	Rarely	Occasionally	Frequently	Almost Constantly
Severity	None	Mild	Moderate	Severe	Very severe
Interference	Not at all	A little bit	Somewhat	Quite a bit	Very much
Present/Absence	No	Yes			

For each selected item from the library: proportion of PRO-CTCAE scores for attributes (frequency, severity and/or interference) will be presented-with stacked bar charts by visit. Maximum PRO-CTCAE score at post-baseline for each item attribute will be summarized by counts and proportions. Proportion of patients with a maximum score of 3 or 4 for each item attribute (severe or very severe, frequently or almost constantly, quite a bit or very much) will also be reported. Proportions will be based on the number of patients with available data and subject with missing response will be excluded from analysis. A listing of the PRO-CTCAE score will be provided for each attribute (frequency, severity, interference, presence).

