
 
To assess anti-drug antibodies (ADAs) against belantamab mafodotin
 
	
 
Incidence and titers of ADAs against belantamab mafodotin
 

 
To evaluate the tolerability of belantamab mafodotin vs pom/dex based on self-reported symptomatic adverse effects
 
	
 
Symptomatic adverse effects as measured by the PRO-CTCAE and OSDI
 

 
To evaluate and compare changes in symptoms and health-related quality of life (HRQOL) of belantamab mafodotin to pom/dex.
 
	
 
Change from baseline of Health-related QOL as measured by EORTC QLQ-C30, EORTC IL52* and EORTC QLQ-MY20*
 

 
To assess Minimal Residual Disease (MRD) in participants who achieve <math>\geq</math>VGPR or better for belantamab mafodotin vs pom/dex
 
	
 
MRD negativity rate, defined as; the percentage of participants who are MRD negative by NGS method
 

Exploratory	

CCI

CCI

ADA= anti-drug antibodies; AE = adverse event; CCI; CCI; CCI; DOR = duration of response; CCI; EORTC-IL52 = Disease Symptoms domain of EORTC QLQMY20; EORTC QLQC30 = European Organisation for Research and Treatment of Cancer Quality of Life Questionnaire 30 item Core module; EORTC QLQMY20 = European Organisation for Research and Treatment of Cancer Quality of Life Questionnaire 20 item Multiple Myeloma module; CCI; CCI; HRQoL = health related quality of life; IMWG = International Myeloma Working Group; KVA = Keratopathy Visual Acuity; MRD = minimal residual disease; NGS = Next Generation Sequencing; ORR = overall response rate; OS = overall survival; OSDI = Ocular Surface Disease Index; PD = progressive disease; PFS = progression-free survival; CCI; CCI; pom/dex = pomalidomide/dexamethasone; PR = partial response; PROCTCAE = Patient Reported Outcomes version of the Common Terminology Criteria for Adverse Events; QOL = quality of life; RRMM = relapsed/refractory MM; SAE = serious adverse event; CCI; TTP = time to progression; TTR -= time to response; VGPR= very good partial response  
\* = EORTC IL52 applies to participants enrolled under the original protocol; EORTC QLQ-MY20 applies to participant enrolled under protocol amendment 1;

CCI

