**Ocular Surface Disease Index**

The Ocular Surface Disease Index (OSDI) is a 12-item questionnaire designed to assesses both the frequency of dry eye symptoms and their impact on vision-related functioning [Schiffman, 2000; Dougherty, 2011]. The OSDI has demonstrated good reliability, validity, sensitivity, and specificity, and can be used as a complement to other clinical and subjective measures of dry eye disease by providing a quantifiable assessment of dry eye symptom frequency and the impact of these symptoms on vision-related functioning.

For the OSDI, the total score will be calculated as well as scores for the three subscales (Ocular Symptoms: item 1-3; Vision-related Function: item 4-9; and Environmental Triggers: item 10-12).

The total OSDI score = ([sum of scores for all questions answered × 100]/[total number of questions answered ×4]). Subscale scores are computed similarly with only the questions from each subscale used to generate its own score. A score of 100 corresponds to complete disability (a response of “all of the time” to all questions answered), while a score of 0 corresponds to no disability (a response of “none of the time” to all questions answered). Therefore, decrease in score from baseline means improvement.

For total score and each of the three sub-scales, the descriptive summary of the actual value and change from baseline at selected time points will be provided. Plots of mean change from baseline (including baseline) and 95% confidence interval over time by visit, and at end of study treatment, last follow-up, and worst case post-baseline for individual domains will also be provided.

***European Organization for Research and Treatment of Cancer Quality of Life Questionnaire 30-item Core Module (EORTC QLQ-C30)***

The EORTC QLQ-C30 is a 30-item questionnaire containing both single- and multi-item measures [Aronson, 1993]. These include five functional scales (Physical, Role, Cognitive, Emotional, and Social Functioning), three symptom scales (Fatigue, Pain, and Nausea/Vomiting), a Global Health Status/QoL scale, and six single items (Constipation, Diarrhea, Insomnia, Dyspnea, Appetite Loss, and Financial Difficulties). Scores for each scale and single-item measure are averaged and transformed linearly to a score ranging from 0–100. Details of deriving domain scores (9 scales and 6 single items) and summary score can be found in Section 6.2.8.1 and more details will be provided in OPS document.

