**Compliance of PRO-CTCAE, OSDI, EORTC QLQ-C30, EORTC QLQ-MY20 and EORTC QLQ-IL52**

For each of the PROs PRO-CTCAE, OSDI, EORTC QLQ-C30, EORTC QLQ-MY20 and EORTC IL52, overall compliance and compliance by visit will be summarized, based on the following definitions.

[figure not shown]
- Number of patients expected to complete PRO form: Date of study discontinuation and/or date of death will be used to determine the last visit at which a patient is still expected under PRO follow-up.
- Evaluable forms:
  - PRO-CTCAE: with at least one non-missing item score
  - OSDI: with at least one non-missing total score or subscale score
  - EORTC QLQ-C30, EORTC QLQ-MY20: with at least one non-missing scale/domain score
  - EORTC IL52: with non-missing EORTC IL52 scale/domain score

The overall compliance rate is defined as the number of patients with an evaluable baseline form and at least one evaluable post-baseline form, divided by the number of patients expected to complete the baseline form.

Compliance by visit will be calculated as the number of patients with an evaluable form at that visit, divided by the number of patients expected to complete the form at that visit.

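### PRO-CTCAE maximum scores ignore the participant's own baseline, so symptoms present before the first dose count under an endpoint of symptomatic adverse effects

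*SAP*

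**What the plan says.** Section 1.1.1 sets a tolerability objective based on self-report, with the endpoint "Symptomatic adverse effects as measured by the PRO-CTCAE and OSDI". Section 4.3.5 describes PRO-CTCAE as a tool for "descriptive reporting of symptomatic treatment side effects in cancer clinical trials" and plans four outputs:

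- stacked bar charts of item scores by visit;
- the raw maximum: "Maximum PRO-CTCAE score at post-baseline for each item attribute will be summarized by counts and proportions";
- the high-score share: "Proportion of patients with a maximum score of 3 or 4 for each item attribute";
- a listing of scores.

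The denominator rule is "Proportions will be based on the number of patients with available data and subject with missing response will be excluded from analysis". It sets no condition on the baseline form or the baseline score.

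A baseline form is expected. The compliance definition at the end of section 4.3.5, which covers PRO-CTCAE, counts "number of patients with an evaluable baseline form and at least one evaluable post-baseline form".

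For OSDI, the other instrument under the same objective, section 4.3.5 states that "the descriptive summary of the actual value and change from baseline at selected time points will be provided". Section 4.5.4.1 counts CTCAE-graded laboratory tests when the worst post-baseline grade is higher than the baseline grade.

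**The concern.** The endpoint label and the description of the instrument both point to effects of treatment. The planned statistic measures something broader: how many participants report a high score at any time after baseline, whatever the score was before treatment. Section 1.2 requires at least two prior lines of therapy and progression on, or non-response to, the last one, so some symptoms at entry are plausible.

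Two things are at stake. The percentage in each arm may be read as a rate of symptomatic toxicity when part of it was present before dosing. And with about 214 versus 106 participants, a chance difference between arms in baseline symptoms passes into the comparison, where the maximum-score tables cannot separate it from a treatment effect.

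**Working it through.** **Reading check.** The SAP states no rate, power or sample size for PRO-CTCAE, so there is no figure to reproduce. Its handling of comparable measures is:

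| Measure | Section | Use of baseline |
|---|---|---|
| PRO-CTCAE maximum and 3-4 share | 4.3.5 | none |
| OSDI | 4.3.5 | actual value and change |
| QLQ-C30, QLQ-MY20 | 4.3.5 | actual value and change |
| Laboratory CTCAE grades | 4.5.4.1 | counted if the grade rises from baseline |
| Blood pressure grades | 4.5.4.2 | grade increase |
| Adverse events | 6.2.3 | treatment-emergent only |

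No readable section supplies a baseline condition for the PRO-CTCAE maximum.

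**Illustration of size.** Inputs:

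- Arm sizes 214 and 106, from section 1.2. These are randomised numbers; the analysis uses Safety Set participants with available data, so actual denominators may be smaller.
- b, the share at 3-4 at baseline: 5% to 30%, assumed. All of them are taken to score 3-4 again at least once without exceeding their baseline score.
- w, the share of the remaining participants who newly reach 3-4: 10%, assumed.

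Formulas:

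- planned share = b + (1 - b)w
- pre-existing part = b / planned share
- newly reached, over all patients = (1 - b)w
- SD of chance baseline imbalance = sqrt[b(1 - b)(1/214 + 1/106)]

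| b | Planned share | Pre-existing part | Newly reached | SD of imbalance (points) |
|---|---|---|---|---|
| 5% | 14.5% | 34% | 9.5% | 2.6 |
| 10% | 19.0% | 53% | 9.0% | 3.6 |
| 20% | 28.0% | 71% | 8.0% | 4.8 |
| 30% | 37.0% | 81% | 7.0% | 5.4 |

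**How imbalance carries through.** Suppose the arms differ at baseline by d, with the same w in both and no treatment effect. The raw difference is d(1 - w) and the baseline-adjusted difference is -dw. With w = 10%, b about 30% and d = 5.4 points (one SD), the raw tables show 5.4 x 0.9 = 4.9 points and the adjusted table shows -0.5 points.

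**Effect on the arm difference.** With equal b in both arms, the raw difference is (1 - b)(w1 - w2). The adjusted difference over all patients is (1 - b)w1 - (1 - b)w2, the same quantity. With w = 20% versus 10%:

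- b = 10%: raw 28% vs 19%, adjusted 18% vs 9%; 9 points both ways.
- b = 30%: raw 44% vs 37%, adjusted 14% vs 7%; 7 points both ways.

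The standard error does change. At b = 30%:

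- raw: sqrt(0.44 x 0.56/214 + 0.37 x 0.63/106) = 5.8 points
- adjusted: sqrt(0.14 x 0.86/214 + 0.07 x 0.93/106) = 3.4 points

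**The case against.** PRO-CTCAE items are scored 0 to 4, or yes/no, unlike the 0-100 scores of OSDI and the EORTC scales. Distributions and maxima are a legitimate descriptive choice, and the plan calls the statistic a post-baseline maximum without any rule attributing it to treatment. The section does not rank its outputs. The bar charts by visit may well include baseline, all scores are listed, and section 1 leaves display details to a separate specification that is not at hand. Both arms follow the same rule, randomisation balances baseline on average, and nothing here is formally tested.

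Most of this stands and limits the weight of the point. It does not remove it: the SAP does not say that the charts include baseline, and neither charts nor listing correct the maximum-score tables. The ordinal scale is no obstacle either, since section 4.5.4.1 already applies a rise-from-baseline rule to graded laboratory data.

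Three stronger readings are tempting and not supported:

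- A reader might infer that myeloma symptoms are being booked as toxicity. The SAP does not name the selected items, so their overlap with disease symptoms is unknown. Only pre-existing symptoms, of whatever cause, can be claimed.
- A reader might infer that the raw maximum dilutes the arm difference and that adjustment restores it. The arithmetic above shows the same difference over all patients.
- A reader might infer that the raw maximum should be replaced. Setting unchanged scores to 0 hides persistent severe symptoms, and a participant at 4 at baseline can never count.

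**Conclusion.** The point holds as a cheap improvement to a descriptive, supportive endpoint. Followed as written, section 4.3.5 counts an unchanged pre-dose score of 3 or 4 under symptomatic adverse effects. That inflates the absolute rates in both arms and leaves chance baseline imbalance in the comparison, in contrast to the SAP's treatment of laboratory grades and OSDI.

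Under the assumed 5% to 30% baseline prevalence and 10% new onset, about a third to four fifths of the reported 3-4 share would be pre-existing. The true fraction depends on a prevalence that the SAP does not give, and it is lower if some participants with high baseline scores improve and stay improved. Adjustment makes the absolute rates interpretable as worsening, removes most of the baseline imbalance and reduces variance; it does not enlarge the difference. PFS, OS and the alpha hierarchy are untouched.

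**What to change.** In the PRO-CTCAE part of section 4.3.5:

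1. Beside the raw maximum, define a baseline-adjusted maximum for each item attribute: the post-baseline maximum if it exceeds the participant's own baseline score, otherwise 0.
2. Report the share with an adjusted maximum of 3 or 4 by arm, next to the raw share.
3. Show the distribution of baseline scores by arm, or state that the by-visit charts include baseline.
4. State a rule for a missing baseline form, for example exclusion from the adjusted table with the number excluded reported by arm. Assuming a score of 0, as section 4.5.4.1 does for laboratory grades, would bring the raw maximum back for those participants.
5. Keep the raw maximum, because only it shows persistent severe symptoms.

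The cost is one derived variable and one extra table per item. A baseline form is already expected, so no new data are needed.

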**Ocular Surface Disease Index**

The Ocular Surface Disease Index (OSDI) is a 12-item questionnaire designed to assesses both the frequency of dry eye symptoms and their impact on vision-related functioning [Schiffman, 2000; Dougherty, 2011]. The OSDI has demonstrated good reliability, validity, sensitivity, and specificity, and can be used as a complement to other clinical and subjective measures of dry eye disease by providing a quantifiable assessment of dry eye symptom frequency and the impact of these symptoms on vision-related functioning.

For the OSDI, the total score will be calculated as well as scores for the three subscales (Ocular Symptoms: item 1-3; Vision-related Function: item 4-9; and Environmental Triggers: item 10-12).

The total OSDI score = ([sum of scores for all questions answered × 100]/[total number of questions answered ×4]). Subscale scores are computed similarly with only the questions from each subscale used to generate its own score. A score of 100 corresponds to complete disability (a response of “all of the time” to all questions answered), while a score of 0 corresponds to no disability (a response of “none of the time” to all questions answered). Therefore, decrease in score from baseline means improvement.

For total score and each of the three sub-scales, the descriptive summary of the actual value and change from baseline at selected time points will be provided. Plots of mean change from baseline (including baseline) and 95% confidence interval over time by visit, and at end of study treatment, last follow-up, and worst case post-baseline for individual domains will also be provided.

***European Organization for Research and Treatment of Cancer Quality of Life Questionnaire 30-item Core Module (EORTC QLQ-C30)***

The EORTC QLQ-C30 is a 30-item questionnaire containing both single- and multi-item measures [Aronson, 1993]. These include five functional scales (Physical, Role, Cognitive, Emotional, and Social Functioning), three symptom scales (Fatigue, Pain, and Nausea/Vomiting), a Global Health Status/QoL scale, and six single items (Constipation, Diarrhea, Insomnia, Dyspnea, Appetite Loss, and Financial Difficulties). Scores for each scale and single-item measure are averaged and transformed linearly to a score ranging from 0–100. Details of deriving domain scores (9 scales and 6 single items) and summary score can be found in Section 6.2.8.1 and more details will be provided in OPS document.

- A high score for functional scales and for Global Health Status/QoL and summary score represent better functioning ability or Health-Related Quality of Life (HRQoL), (higher score indicates improvement)
- whereas a high score for symptom scales and single items represents significant symptomatology [Proskorovsky, 2014]. (lower score indicates improvement)

Descriptive summaries (mean, SD, median, min and max) of the actual value and change from baseline at selected time points will be provided for EORTC QLQ-C30 summary score and each domain score. The number and percentage of participants with post-baseline score improved by  $\geq 10$ , and  $\geq 5$  points, respectively from baseline score will be summarized at selected time points. The number and percentage will be provided for summary score and each domain score. Should new thresholds be available at the time of the analysis (i.e. from ongoing EORTC group work) these modified thresholds will be used and specified in OPS.

Plots of mean change from baseline (including baseline) and 95% confidence interval over time by visit, and at end of study treatment, last follow-up, and worst case post-baseline for individual domain score and summary scores will also be provided.

Longitudinal changes from baseline by treatment group for EORTC QLQ-C30 domain Fatigue will be explored using a restricted maximum likelihood-based mixed model for repeated measures (MMRM) to compare between-treatment difference adjusting for correlations across multiple time points within a patient and controlling for the baseline value. Adjusted mean difference and 95% CIs will be presented to illustrate the effect of treatment.

The MMRM model will include patient, treatment, analysis visit, and treatment-by-visit interaction as explanatory variables, the baseline value as a covariate along with the baseline-by-visit interaction. Treatment, visit, and treatment-by-visit interactions will be fixed effects in the model; patient will be treated as a random effect. An unstructured

covariance matrix will be used to model the within subject variance and the Kenward-Roger approximation will be used to estimate the degrees of freedom. Restricted maximum likelihood (REML) estimation will be used. If the fit of the unstructured covariance structure fails to converge, the following covariance structures will be used in order until convergence is reached: toeplitz with heterogeneity (TOEPH), autoregressive with heterogeneity (ARH(1)), Toeplitz (TOEP), and autoregressive (AR(1)). If there are still issues with the fit of the model or estimation of the treatment effects, SUBJECT will be treated as a fixed effect.

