## 1.2. Study Design

Overview of Study Design and Key Features	

* Progression (a) on, or within 60 days of completion of the last therapy or (b) must be non-responsive while on last treatment, where non-responsive is defined as not achieving at least Minimal Response (MR) after 2 complete treatment cycles
 
** Stratification based on International Staging System (ISS), number of prior lines of therapy and prior usage of anti-CD38 antibody treatment
 
*** Until progressive disease (PD), death, unacceptable toxicity, withdrawal of consent, lost to follow-up or end of study, whichever comes first
	

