## **4. STATISTICAL ANALYSES**

### **4.1. General Considerations**

#### **4.1.1. General Methodology**

The Intent-to-Treat (ITT) analysis set will be used for all study population analyses and efficacy analyses, unless otherwise specified and Safety analysis set will be used for all safety analyses.

The stratified log-rank test and stratified Cox proportional hazards models will include the randomization stratification factors as “strata”. Unless otherwise specified, the stratification factors entered for randomization will be used in the primary analysis. If there is any mis-stratification, a supplementary analysis will be performed using the stratification data based on the clinical database.

Confidence intervals will use 95% confidence levels unless otherwise specified.

Unless otherwise specified, continuous data will be summarized using descriptive statistics: n, mean, standard deviation (std), median, minimum and maximum. Categorical data will be summarized as the number and percentage of participants in each category.

For efficacy analyses, only central lab values will be used.

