Longitudinal changes from baseline by treatment group for EORTC QLQ-IL52 domain score will be explored using a restricted maximum likelihood-based mixed model for repeated measures (MMRM), using the same approach described in Section for EORTC QLQ-C30 analysis.

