### 4.6.2. Subgroup analyses

#### 4.6.2.1. Subgroup analyses of PFS

Subgroup analyses of PFS will be based on the ITT analysis set.

The following subgroup analyses will be performed to compare the primary estimand of PFS between treatments, based on investigator-assessed response, respectively, if data permit.

Subgroup	Categories 
Previous treatment with anti-CD38 therapy 	Yes, No
ISS staging 	I/II; III
Number of prior lines of therapy 	≤3; >3
Previous treatment with anti-CD38 therapy and number of prior lines of therapy	Yes and >3; Other
Previous treatment with melphalan	Yes, No
Previous stem cell transplant	Yes, No
Age at randomization	<65, ≥65 to <75, ≥75 years age
Gender	Male, Female
Ethnicity	Hispanic, Non-Hispanic
Race	Black, White, Other
Region of Enrollment	North America, Europe, North East Asia, Rest of the world
Baseline renal impairment status per eGFR (ml/min/1.73 m  )	Normal (≥ 90), Mild (≥ 60, < 90), Moderate (≥ 30, < 60), Severe (≥ 15, < 30)
Type of myeloma	IgG, Non-IgG

Subgroup	Categories 
Baseline extramedullary disease	Yes, No
Cytogenetics Risk 	High, Other (non-high risk - all others)
Refractory to prior anti-cancer therapy	Any Proteasome Inhibitor (PI) Bortezomib Carfilzomib Ixazomib Any Immunomodulator (IMiD) Thalidomide Lenalidomide Pomalidomide Any Monoclonal Antibody Elotuzumab Isatuximab Daratumumab Daratumumab alone  Daratumumab in combination  PI+IMiD Anti-CD38 antibody+PI+IMiD

- [1]. If the percentage of participants is small within a particular subgroup, then the subgroup categories may be refined prior to unblinding the trial.
- [2]. Randomization factors
- [3]. A subject is considered as high risk if the subject has any of the following cytogenetics: t(4;14), t(14;16), and del(17p13).
- [4]. Defined as prior CTX regimen with Daratumumab as the only drug in the regimen.c
- [5]. Defined as prior CTX regimen with Daratumumab and other drugs.

Additional subgroups CCI may be assessed if there is clinical justification or an imbalance is observed between the treatment arms. The purpose of the subgroup analyses is to assess the consistency of treatment effect across expected prognostic factors.

The ITT analysis set will be used in the subgroup analyses. The subgroup analyses will be based on values recorded on the eCRF (or vendor data if collected outside of eCRF).

CCI

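### The MMRM for QLQ-C30 Fatigue and IL52 omits the three randomisation factors, so its intervals are somewhat too wide if those factors predict the scores

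*SAP*

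**What the plan says.** SAP Section 4.3.5 lists the terms of the QLQ-C30 Fatigue model: "The MMRM model will include patient, treatment, analysis visit, and treatment-by-visit interaction as explanatory variables, the baseline value as a covariate". The list closes with an interaction of baseline and visit. Within-subject covariance is unstructured, with fallback structures if the fit does not converge. For IL52 the SAP specifies an MMRM "using the same approach described in Section for EORTC QLQ-C30 analysis", so the same terms apply.

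Section 1.2 gives the randomisation factors: "Stratification based on International Staging System (ISS), number of prior lines of therapy and prior usage of anti-CD38 antibody treatment". The levels are yes/no for anti-CD38, I/II against III for ISS, and ≤3 against >3 for prior lines. Section 4.1.1 says where they enter the analysis: "The stratified log-rank test and stratified Cox proportional hazards models will include the randomization stratification factors". It does not mention the MMRM.

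On status, Section 4.3.5 says: "Longitudinal changes from baseline by treatment group for EORTC QLQ-C30 domain Fatigue will be explored using a restricted maximum likelihood-based mixed model". The output is an adjusted mean difference with a 95% CI. Section 2.1 restricts type I error control to PFS and then OS.

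**The concern.** Randomisation within strata makes the arms alike on the stratifying factors. An analysis that ignores a factor related to the outcome leaves that factor's variance in the residual, so the model-based standard error is larger than the real variability of the estimate. The plan avoids this for its log-rank tests and main Cox models but not for these two MMRMs.

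The second issue is missing data. A likelihood-based MMRM is valid if missingness depends only on what the model conditions on. If ISS stage, prior lines or prior anti-CD38 treatment drive both the score and who stops returning forms, leaving them out makes that condition harder to meet.

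At stake are the width of the intervals and, under further conditions, a small bias in the between-arm differences for two supportive secondary scores.

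**Working it through.** **1. Is there a figure to reproduce?** No. The SAP gives no SD, effect size, power or dropout rate for the MMRM, and nothing on how far the factors predict Fatigue or IL52. Every size below therefore rests on a stated assumption.

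**2. Reported standard error.** Let R² be the share of residual variance, after baseline, that the three factors explain. With balanced factors,

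SE without / SE with = 1/√(1 − R²).

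Three extra parameters cost a factor of √((320 − 6)/(320 − 3)) = √(314/317) = 0.9953, taking all 320 participants of Section 1.2. The cost is larger at late visits with fewer forms.

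| Assumed R² | SE ratio | Reported SE too large by | Ratio net of 3 df |
|---|---|---|---|
| 0 | 1.0000 | 0% | 0.9953 |
| 0.01 | 1.0050 | 0.5% | 1.0003 |
| 0.02 | 1.0102 | 1.0% | 1.0054 |
| 0.05 | 1.0260 | 2.6% | 1.0211 |
| 0.10 | 1.0541 | 5.4% | 1.0491 |
| 0.15 | 1.0847 | 8.5% | 1.0795 |

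**3. Actual variability and bias, by simulation.** The design was 320 participants, 2:1, blocks of six within eight strata, two post-baseline visits with unstructured covariance, about half missing at visit 2, and 3,000 replicates per scenario. Assumptions: factor prevalences of 40%, 30% and 45%; residual SD about 1; each factor shifts the visit-2 score by the amount shown (half that at visit 1). Dropout depends on the factors either equally in both arms (log-odds 0.6 per factor) or in the control arm only (0.9 per factor). The true treatment effect is 0. Results are for visit 2:

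| Shift per factor | Dropout depends on factors | Bias without | Bias with | Sampling SD without / with | Ratio |
|---|---|---|---|---|---|
| 0 | both arms | −0.002 | −0.003 | 0.1582 / 0.1593 | 0.994 |
| 0 | one arm | 0.003 | 0.003 | 0.1612 / 0.1634 | 0.987 |
| 0.1 | both arms | −0.001 | −0.001 | 0.1576 / 0.1584 | 0.995 |
| 0.1 | one arm | 0.022 | 0.003 | 0.1569 / 0.1595 | 0.984 |
| 0.2 | both arms | −0.004 | −0.004 | 0.1551 / 0.1549 | 1.001 |
| 0.2 | one arm | 0.042 | −0.001 | 0.1578 / 0.1589 | 0.993 |
| 0.3 | both arms | 0.006 | 0.006 | 0.1555 / 0.1548 | 1.005 |
| 0.3 | one arm | 0.059 | −0.002 | 0.1577 / 0.1579 | 0.999 |

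Monte Carlo error on each bias is about 0.158/√3000 = 0.003.

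The true sampling SD is nearly the same with and without the factors (ratio 0.98 to 1.01), because randomisation has already balanced them. Step 2 is therefore about the reported SE, which is too large. Bias appears only when the factors shift the score and selection on them differs by arm. It is then 0.02 to 0.06 of an SD, and including the factors removes it. The top value is 0.059/0.158 = 0.37 of the estimate's own sampling SD, in a deliberately one-sided scenario.

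**4. Could selection differ by arm without an arm-specific factor effect?** As an illustration, assume that loss of forms follows the PFS hazards (the SAP does not say so). Let one balanced factor double the hazard in both arms, with control hazards of 0.116 and 0.231 per month (mean 0.173 = ln 2/4) and the planned HR of 0.57. At 6 months the high-risk share of those remaining is e^(−1.386)/(e^(−1.386) + e^(−0.696)) = 33% in control. In the belantamab arm it is e^(−0.790)/(e^(−0.790) + e^(−0.397)) = 40%. A 0.2 SD shift in score then gives 0.2 × 0.07 = 0.014 SD, before conditioning on earlier visits. The direction is possible, but the size is very small.

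**The case against.** The best defence is that nothing here is an error. Section 4.1.1 requires the factors only in the stratified log-rank and Cox analyses, and the SAP uses unstratified Cox models in Sections 4.2.3 and 4.6.2.1. A baseline-adjusted MMRM in a randomised trial is valid. It also conditions on baseline-by-visit and, through the unstructured covariance, on each participant's earlier scores, so missing at random is not bare. The SAP does not show that the factors predict Fatigue or IL52; its remark that subgroup analyses "assess the consistency of treatment effect across expected prognostic factors" concerns PFS. All of this stands. It makes the point conditional and a matter of choice, but it shows no drawback to adding the terms beyond a few degrees of freedom.

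A reader might infer more than the document supports:

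- **Lost participants.** The factor 1/(1 − R²) − 1 gives 1% to 17.6% for R² of 0.01 to 0.15 and could be read as a sample-size equivalent. It is not one, since the estimate's real variability hardly changes.
- **Progression ends PRO collection, so median PFS of 7 against 4 months implies differential dropout.** The compliance rules in Section 4.3.5 tie expected completion to study discontinuation or death, not to progression. Different dropout rates alone are also not enough; selection on the factors must differ by arm.
- **These are the plan's only model-based HRQoL comparisons.** That holds for the visible text only, because Section 4.4 is redacted.

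**Conclusion.** The omission is real and affects both MMRMs. It contradicts no other section. Its main effect is conservative: intervals a few percent too wide at most plausible values of R², provided the factors carry information on the score beyond baseline. A small bias needs three things together: the factors predict the score, they predict missingness, and the resulting selection differs by arm. The SAP establishes none of these, so the R² range and the simulated bias are assumptions, not estimates for this trial. The consequence is minor, because the comparison is exploratory and no PFS or OS conclusion depends on it. It is worth making as a low-cost improvement.

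**What to change.** In Section 4.3.5, add prior anti-CD38 treatment (yes/no), ISS stage (I/II or III) and number of prior lines (≤3 or >3) as fixed effects in the Fatigue MMRM, using the values entered at randomisation, as the primary analysis does. State that the IL52 model carries the same terms. Factor-by-visit interactions are optional; they let the factor effects change over time, as the baseline effect already may.

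The cost is three degrees of freedom for main effects, more with visit interactions. The values already exist for the stratified analyses, so only SAP wording and model code change. Sample size, conduct and the testing hierarchy stay as they are.
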